6.5. Study Intervention Compliance

When participants are dosed at the site, they will receive study intervention directly from the investigator or designee, under medical supervision. The date and time of each dose administered in the clinic will be recorded in the source documents. The dose of study intervention and study participant identification will be confirmed at the time of dosing by a member of the study site staff other than the person administering the study intervention.

When participants self-administer study intervention at home, compliance with study intervention will be assessed at each visit, and a subject diary will be completed. Compliance will be assessed by returned capsules/tablets, the subject diary, and during the site visits and documented in the source documents and relevant form. Deviation(s) from the prescribed dosage

regimen should be recorded. Compliance is deemed acceptable if within 80-120% of the scheduled dosing. A record of the quantity of dispensed study intervention to and administered by each participant must be maintained and reconciled with study intervention and compliance records. Intervention start and stop dates, including dates for intervention delays and/or dose reductions will also be recorded.

6.6. Dose Modification

As shown in the Study Schema (Figure 1), participants randomized to the phenserine arm will initiate dosing at 5 mg bd and maintain this dose for the first two weeks of study treatment. At the Week 3 visit, participants may be escalated to 10 mg bd, then 10mg tds (Figure 1), based on tolerability, including adverse events, clinical assessment, ECG and safety laboratory measurements. Participants who are unable to tolerate a higher dose will have their dose reduced to the next previous dose level and maintained at that dose through the remainder of the study. This clinical decision will be made by the study physician and the study team at each centre at the visit, or when any safety laboratory results are received during the days after the visit. If needed, the medical monitor and the PI will be contacted. All participants are expected to be at their individualized maintenance dose for 4 weeks (beginning of Week 5 through the end of Week 8).

Participants randomized to the donepezil arm, will initiate dosing at 5 mg od and will be evaluated at the Week 4 visit for dose escalation to 10 mg once daily. For participants in the phenserine arm, dosing will follow a stepwise escalation to ensure safety and efficacy:

- **Weeks 1-2:** Participants will begin with 5 mg twice daily (bd).
- **Weeks 3-4:** Participants will escalate to 10 mg twice daily (bd) if the initial dose is well tolerated.
- **Weeks 5-8:** Participants will further escalate to 10 mg three times daily (tds) based on continued tolerability.

Before any dose escalation, the dosage will be reassessed based on tolerability. If necessary, participants may be required to return to the center for a dose reduction. Throughout the study, dose adjustments will be made according to tolerability. Should any dose escalation lead to adverse effects that compromise the participant's well-being or safety, the dose will be reduced to the previously well-tolerated level. Participants will then continue at this adjusted dose for the remainder of the study period. These procedures are outlined in more detail in the dedicated SOP.

6.7. Treatment of Overdose

In the event of an overdose, supportive care and administration of an anticholinergic will be provided, according to current guidelines, to reverse cholinergic effects. Supportive care includes stabilizing the airway, providing intravenous fluids to maintain hydration and blood pressure, and closely monitoring vital signs and neurological status. If a patient experiences a cholinergic overdose at home, it is crucial to seek immediate medical attention by calling emergency services.

Patients and caregivers will be instructed on recognizing symptoms of cholinergic overdose, severe nausea, vomiting, salivation, diarrhea, muscle weakness and sedation.

6.8. Prior and Concomitant Therapy

Any medication or vaccine (including over the counter or prescription medicines, recreational drugs, vitamins, and/or herbal supplements) that the participant is receiving at the time of enrollment or receives during the study must be recorded along with:

- **Reason for use**
- **Dates of administration** including start and end dates.
- **Dosage information** including dose and frequency.

The medical monitor should be contacted if there are any questions regarding concomitant or prior therapy.

Participants must abstain from taking prescription or nonprescription drugs (including vitamins, recreational drugs, and dietary or herbal supplements) within 7 days (or 14 days if the drug is a potential enzyme inducer) or 5 half-lives (whichever is longer) before the start of study intervention until completion of the follow-up visit, unless, in the opinion of the investigator and sponsor, the medication will not interfere with the study.

To ensure participant safety, certain medications or medical conditions known to interact with cholinesterase inhibitors will lead to participant not being included, or excluded is occurring during the study, or used with caution and monitored with particular care during the study:

6.8.1. Contraindications:

- Known hypersensitivity to AChE inhibitors, piperidine derivatives, or any excipients listed in the product formulation. Anaesthesia: AChE inhibitors may exaggerate succinylcholine-type muscle relaxation during anaesthesia and thus surgery requiring anaesthetic will lead to exclusion. Neurological Conditions such as a history of seizures, extrapyramidal symptoms and Neuroleptic Malignant Syndrome

6.8.2. Use with caution

- Cardiovascular conditions, such as QTc prolongation or bradycardia (refer to Exclusion Criteria for detailed monitoring requirements).
- Gastrointestinal risks, including a history of ulcers or concurrent NSAID use (refer to Exclusion Criteria).
- Concomitant Medications: drugs affecting the cholinergic system.

6.8.3. Permitted Medications

- **Paracetamol/Acetaminophen**, at doses of ≤ 2 grams/day, is permitted for use Other concomitant medications may be considered on a case-by-case basis by the investigator in consultation with the medical monitor if required.

6.8.4. Anti-Dementia Drugs

If deemed clinically indicated by the study clinician and the participant, participants currently taking anti-dementia drugs (e.g., donepezil, rivastigmine, galantamine, memantine) can participate in the study after a washout period of at least 4 weeks prior to the start of the study intervention. This is to ensure that there are no residual effects of these medications that could interfere with the study results. The washout period ensures that any pharmacodynamic or pharmacokinetic effects from previous medications are minimized, allowing for a clearer assessment of phenserine and donepezil.

6.8.5. Rescue Medicine

The study site will not supply rescue medication.

7. Monitoring of Study Intervention and Participant Discontinuation/Withdrawal

Participants may choose to withdraw from the study at any time and for any reason. Participants may be withdrawn from the study if it is in their best clinical interest by the site Investigator.

Participants who drop out of the study will be recorded as either defaulters or withdrawn.

‘Defaulters’ are participants who withdraw their consent to participate in the trial, affecting both treatment and assessment. No further assessments can be made of these participants.

‘Withdrawn’ are participants who are withdrawn from treatment at the discretion of the chief investigator because of clinical factors, poor compliance, or a change in circumstances.

Withdrawn participants will remain in the study and trial assessments will still be undertaken.

The reason for dropping out will also be recorded.

Every effort will be made to collect outcome data on all participants who withdraw from treatment for whatever reason. If participants withdraw from treatment, all endpoint assessments will be carried out at the point of drop-out and at the 8-week endpoint unless consent is withdrawn.

This study is unblinded with respect to the treatment assignment so both the participant and site staff will know which treatment modality the participant received.

7.1. Monitoring and discontinuation of Study Intervention

7.1.1. Liver Function Monitoring

1. **Elevated Liver Enzymes (ALT or AST $\leq 5 \times$ ULN):**
 - a. **Action:** Continue the study intervention with closer monitoring. Repeat liver function tests at the next scheduled visit (2 weeks) or sooner if clinically indicated.
 - b. **Clinical Follow-Up:** Investigate potential contributing factors, such as concomitant medications, alcohol intake, or underlying conditions.
 - c. **Adjustment:** Consider reducing the dose of the study drug if levels approach $5 \times$ ULN or if clinical symptoms develop.
2. **Isolated Total Bilirubin Elevation (>1 but $\leq 2 \times$ ULN):**
 - a. **Action:** If ALT or AST levels are normal and there are no signs of liver injury, continue the study intervention with follow-up testing at the next visit.
3. **Clinical Symptoms Without Significant Enzyme Elevation:**
 - a. **Action:** If participants report symptoms such as nausea, fatigue, or right upper quadrant discomfort without significant liver enzyme elevation, monitor closely, evaluate for alternate causes, and repeat tests as clinically indicated.

7.1.1.1. Liver Function Stopping Criteria

1. **ALT or AST Elevation:**
 - Discontinue the study intervention if ALT or AST levels are greater than 3 times the upper limit of normal (ULN) in conjunction with an increase in total bilirubin greater than 2 times the ULN (with > 35% direct bilirubin) or if the participant shows signs or symptoms of liver injury (e.g., jaundice).
 - Discontinue if ALT or AST levels are greater than 3 times the ULN and the international normalized ratio (INR) is greater than 1.5 (if INR is measured), which may indicate severe liver injury (possible Hy's law).
2. **Severe Elevation of Liver Enzymes:**
 - Discontinue if ALT or AST levels are greater than 8 times the ULN, regardless of other symptoms.
3. **Persistent Elevation:**
 - Discontinue if ALT or AST levels are persistently greater than 5 times the ULN for more than 2 weeks.
4. **Total Bilirubin Elevation:**
 - Discontinue if total bilirubin is greater than 2 times the ULN, especially if associated with elevated ALT or AST levels.
5. **Signs and Symptoms of Liver Injury:**
 - Discontinue if the participant exhibits clinical signs of liver injury such as jaundice, dark urine, significant right upper quadrant pain, or unexplained nausea/vomiting.
6. **Investigator's Discretion:**
 - Discontinue if the investigator deems it necessary based on their clinical judgment, even if the specific criteria above are not met.

7.1.2. Renal Function Monitoring and Management

1. **Reduced eGFR (≥ 30 but < 90 mL/min/1.73 m²):**
 - a. **Action:** Continue the study intervention with follow-up testing at the next scheduled visit (2 weeks). Encourage hydration if clinically appropriate.
 - b. **Clinical Follow-Up:** Assess for reversible causes, such as dehydration, urinary obstruction, or nephrotoxic medications.

7.1.2.1. Renal Function Stopping Criteria

1. **Severe Reduction in Renal Function:**
 - Discontinue if the estimated glomerular filtration rate (eGFR) falls below 30 mL/min/1.73 m².
2. **Acute Kidney Injury:**
 - Discontinue if there is evidence of acute kidney injury, defined as:
 - An increase in serum creatinine by 1.5 times the baseline value within 7 days, or
 - A reduction in urine output (oliguria) for more than 6 hours.

3. Signs and Symptoms of Renal Dysfunction:
 - Discontinue if the participant exhibits clinical signs of renal dysfunction, such as significant edema, oliguria, or unexplained fatigue accompanied by abnormal renal markers.
4. Investigator's Discretion:
 - Discontinue if the investigator determines that renal function decline poses a risk to the participant, even if specific thresholds above are not met.

7.1.3. ECG Monitoring and Management:

1. Continuous monitoring of heart rate and rhythm will be conducted every 2 weeks during regular medical evaluations.
2. QTc interval ≥ 460 milliseconds for males or ≥ 470 milliseconds for females will be considered abnormal during the ECG assessments. If this happens, frequency of ECG monitoring will be increased by investigator's discretion and dose reduction or study withdrawal will be considered.
3. Electrolyte levels (e.g., potassium, magnesium) will be monitored to identify factors contributing to QTc prolongation.

7.1.3.1. ECG Stopping Criteria:

1. **Severe Bradycardia or Arrhythmias:**
 - Discontinue if heart rate falls below 50 bpm, significant arrhythmias are detected, or participants experience syncope due to heart block or long sinus pauses.
2. **QTc Prolongation:**
 - QTc >500 ms for both genders.

7.1.4. Gastrointestinal monitoring and management:

1. Assess participants for gastrointestinal symptoms, including abdominal pain, nausea, vomiting, diarrhea, or signs of GI bleeding (e.g., melena, hematemesis), at every 2-week visit.
2. Participants with a history of peptic ulcer disease or taking NSAIDs will have their gastrointestinal status assessed more closely, including monitoring for dyspepsia or signs of ulceration.

7.1.4.1. Gastro intestinal Stopping Criteria:

1. **GI Bleeding or Ulceration:**
 - Discontinue if participants exhibit confirmed GI bleeding (e.g., melena, hematemesis).
2. **Persistent Severe Symptoms:**

- Discontinue if participants experience persistent severe gastrointestinal symptoms (e.g., uncontrolled vomiting, abdominal pain) that do not resolve with symptomatic management.

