4.1. Overall Design

Consented patients will undergo a screening visit within 28 days of the planned baseline visit. (For women of childbearing potential, a negative serum pregnancy test will be required within 1 day prior to receiving the first dose of study drug). Only those patients who complete screening and meet study eligibility criteria at baseline will be randomized 6:2 to receive phenserine or donepezil in an open-label manner. The first dose of study medication will be taken in the clinic, and the participant will be instructed on how to continue dosing at home until their next visit.

Participants will visit the clinic for safety and other planned study assessments at 2-week intervals through the 8-week treatment period, as detailed in the Schedule of Activities ([Table 1](#)).

Patients who withdraw or discontinue from the study before Week 8 will have an early termination visit within one week of discontinuation that includes safety follow-up. For participants who complete the study, a final follow-up safety assessment will be conducted within one week after completion of dosing.

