7.2. Procedures for Participant Discontinuation

In rare instances, it may be necessary for a participant to permanently discontinue the study intervention. If the study intervention is permanently discontinued, the participant should, if at all possible, remain in the study to be evaluated for safety, tolerability, and efficacy outcomes. See the Schedule of Assessments (SoA) for data to be collected at the time of discontinuation of study intervention and follow-up, and for any further evaluations that need to be completed. Participants who discontinue the study intervention should undergo the following procedures:

1. **Documentation of Reason for Discontinuation:** The reason for discontinuation must be documented in detail, including any adverse events, lack of efficacy, non-compliance, or personal reasons.
2. **Outcome data:** Every effort will be made to collect outcome data on all participants who withdraw from treatment for whatever reason. If participants withdraw from treatment, all endpoint assessments will be carried out at the point of drop-out and at the 12-month endpoint unless consent is withdrawn.

As PATH-1 is unblinded there will be no procedures related unblinding of the participants

8. Required Actions and Follow-Up

1. Reporting:

- All events of ALT or AST $\geq 3 \times$ ULN and total bilirubin $\geq 2 \times$ ULN (with $> 35\%$ direct bilirubin) or ALT or AST $\geq 3 \times$ ULN and INR > 1.5 or GFR < 30 mL/min/1.73 m²) and acute kidney injury (e.g., serum creatinine increase by 1.5 times baseline or oliguria) must be reported to the sponsor in an expedited manner.
- Additionally, QTc prolongation ≥ 460 milliseconds for males or ≥ 470 milliseconds for females, significant arrhythmias (e.g., Torsade de Pointes), or bradycardia with heart rate < 50 bpm and associated symptoms (e.g., syncope) must also be reported within 24 hours. Confirmed gastrointestinal bleeding, such as melena, hematemesis, or peptic ulcers, persistent severe symptoms not resolving with management (e.g., uncontrolled vomiting), should be reported as serious adverse events (SAEs) when applicable. All adverse events must be documented in the case report form (CRF) and reported to the study sponsor regulatory authorities according to local requirements.

2. Follow-Up

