- Repeat laboratory or clinical assessments (e.g., liver enzymes, eGFR, ECGs, or GI evaluations) will be conducted weekly or bi-weekly, depending on the severity of the abnormality, until resolution or stabilization.
- Comprehensive clinical evaluations, including symptom assessments, will be performed as needed.

3. Continuation of the study intervention

- Continuation of the study intervention of the study intervention will be considered only if the abnormality resolves or improves to a clinically acceptable level, as determined by the investigator and sponsor.

4. Participant communication: Participants will be informed of the findings, any changes to their treatment plan, and the rationale for either resuming or discontinuing the study intervention.

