8.1.1. Temporary Discontinuation

Abnormalities identified during regular monitoring, including but not limited to liver chemistry changes, renal function decline, cardiac abnormalities (e.g., QTc prolongation), or gastrointestinal symptoms, will be assessed by the investigator to determine the appropriate course of action. This may include enhanced monitoring, additional diagnostic evaluations, or discontinuation of the study intervention.

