8.1.2. Study Intervention Restart or Rechallenge After Stopping Criteria Are Met

Study intervention restart or rechallenge in participants who have met stopping criteria for liver chemistry, ECG abnormalities, renal dysfunction, or other safety-related are not allowed.

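### The 7-day limit in the creatinine stopping rule cannot be met by scheduled on-treatment samples, so a 1.5-fold rise first found at a two-weekly visit does not trigger the automatic stop

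*Protocol*

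**What the plan says.** **The stopping rule.** Protocol 7.1.2.1 lists the renal reasons to discontinue. Acute kidney injury has two alternative limbs. The creatinine limb is "An increase in serum creatinine by 1.5 times the baseline value within 7 days, or"; the other is oliguria lasting more than 6 hours. Separate criteria are eGFR below 30, clinical signs of renal dysfunction, and investigator judgement. Under 8.1.2, study drug "restart or rechallenge in participants who have met stopping criteria for liver chemistry, ECG abnormalities, renal dysfunction, or other safety-related are not allowed".

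**The sampling.** The Schedule of Activities (1.3, footnote 8) has renal function taken at every visit. On-treatment visits are Weeks 2, 4, 6 and 8, each ±3 days; SAP 2.4 gives the same windows. The safety-laboratory row is marked at screening but blank at baseline, although footnote 8 implies a draw then.

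**Management below the stop.** For eGFR from 30 to below 90, 7.1.2 says "Continue the study intervention with follow-up testing at the next scheduled visit (2 weeks"), with a check for reversible causes. It makes no exception for a 1.5-fold creatinine rise and does not refer to Section 8.

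**Section 8.**
- Item 1 (reporting): "acute kidney injury (e.g., serum creatinine increase by 1.5 times baseline or oliguria) must be reported to the sponsor in an expedited manner". It has no 7-day limit.
- Item 2 (follow-up): repeat assessments "will be conducted weekly or bi-weekly, depending on the severity of the abnormality".
- Item 3: continuing the study drug "will be considered only if the abnormality resolves or improves to a clinically acceptable level, as determined by the investigator and sponsor".
- 8.1.1, on abnormalities found in monitoring: "This may include enhanced monitoring, additional diagnostic evaluations, or discontinuation of the study intervention".

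Protocol 2.3.1 names stopping criteria for kidney function among the measures that protect participants.

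**The concern.** A stopping criterion tied to a laboratory value should be capable of being met by the samples the protocol schedules. Here the time limit is shorter than the shortest interval between scheduled on-treatment samples. The usual way a creatinine rise would come to light, a routine two-weekly blood test, therefore falls outside the numeric rule.

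The site must then decide what else applies. 7.1.2 points towards continuing. Section 8 items 1 and 3, read together, point towards continuing only after improvement and with the sponsor involved. Nothing says which takes precedence. What is at stake is consistency across six centres in applying a rule that the protocol presents as a safeguard. The commonest expected side effects are nausea, vomiting and diarrhoea (2.2, 4.3), and 7.1.2 itself lists dehydration as a reversible cause of reduced eGFR, so the situation is not far-fetched.

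**Working it through.** **1. Inputs.** Visit targets are Day 0 and Days 14, 28, 42 and 56; the last four have ±3-day windows (Protocol 1.3; SAP 2.4). Screening is within the 28 days before baseline. The limb needs a 1.5-fold rise within 7 days (7.1.2.1).

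**2. Gaps between adjacent on-treatment samples** (Weeks 2–4, 4–6, 6–8).
- Minimum = (next target − 3) − (previous target + 3) = (28 − 3) − (14 + 3) = 25 − 17 = 8 days.
- Nominal = 28 − 14 = 14 days.
- Maximum = (28 + 3) − (14 − 3) = 31 − 11 = 20 days.

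Each pair has 7 × 7 = 49 combinations of visit days, and 0 of 49 give a gap of 7 days or less.

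**3. Gap from the pre-treatment value to Week 2.**
- From Day 0: 14 − 3 = 11 to 14 + 3 = 17 days.
- From screening: 11 days (screened on Day 0) to 17 + 28 = 45 days.

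Whether *baseline* means the pre-treatment value or the last lower value, no scheduled on-treatment sample lies within 7 days of it. Nor does 7.1.2.1 allow a rise to be presumed to have occurred within 7 days.

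**4. Ways the limb could still be met.**
- An unscheduled sample in the first week after Day 0.
- A weekly repeat of a smaller rise that then progresses, but only if the comparison is with the last lower value; the pre-treatment value would normally be more than 7 days old by then.
- The follow-up visit. Under 4.1, for completers "a final follow-up safety assessment will be conducted within one week after completion of dosing"; the Schedule of Activities allows 28 days. The early-termination visit is also within one week of discontinuation. In both cases dosing has already ended.

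**5. Does the eGFR stop catch these rises?** The documents give no eGFR equation. Assume eGFR varies with creatinine to the power −k, with k from 1 to 1.2. A 1.5-fold rise multiplies eGFR by 1.5^−1 = 0.667 to 1.5^−1.2 = 0.615. The starting eGFR that lands exactly on 30 is 30 × 1.5 = 45.0 to 30 × 1.5^1.2 = 48.8. From starting values of 50 to 105 the result is about 31 to 70. So above a starting eGFR of about 45 to 49 the eGFR stop is not reached, and results of this size fall in the band where 7.1.2 says to continue.

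**6. The same result under each section** (1.5-fold rise, first found at Week 2, 4 or 6, eGFR 30 to below 90, no symptoms).

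| Section | Instruction |
|---|---|
| 7.1.2.1, creatinine limb | Not met: no value within the previous 7 days |
| 7.1.2 | Continue; retest at the next visit; look for reversible causes |
| Section 8 item 1 | Acute kidney injury; expedited report |
| Section 8 item 3 | Continue only if resolved or improved, as judged by investigator and sponsor |

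**The case against.** The strongest reply is that 7.1.2 does not stand alone. Protocol 3.2.2 and 6.6 base dose decisions on safety laboratory results, including results that arrive after the visit. Footnote 5 of the Schedule of Activities allows recall for a lower dose. Protocol 9.15 requires documented laboratory review and repeats of clinically significant abnormal values, and 9.17 requires a decision on reducing, pausing or withdrawing when an adverse event warrants it. Section 9 permits unscheduled samples. Investigator discretion in 7.1.2.1 applies even when no threshold is met. 4.4.4 and 6.6 also refer to an SOP on dose handling that is not available here. All of this stands, and it rules out three stronger readings.

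- **That the drug cannot be stopped for a creatinine rise.** The documents say otherwise, by the routes just listed and by eGFR below 30, oliguria, clinical signs, 8.1.1 and Section 8 item 3.
- **That Section 8 item 1 contradicts 7.1.2.** Item 1 is a reporting rule; reporting a rise and continuing the drug are compatible. Its part is to call the rise acute kidney injury without a time limit, which brings item 3 into play. Item 3 might itself be read as governing restart after a hold, since item 4 beside it speaks of resuming or discontinuing. Even so, no text says how it relates to 7.1.2.
- **That a participant reported as having acute kidney injury would be dosed for another 8 to 20 days.** At 10 mg tds that would be 3 × 14 = 42 capsules nominally (24 to 60), and at 10 mg bd 2 × 14 = 28 (16 to 40). This requires a site that reports under Section 8 while ignoring the items that follow, and that makes no laboratory-based dose decision. It cannot follow a Week 8 finding, because dosing ends there. It is an outer limit for Weeks 2, 4 and 6, not an expected outcome.

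It can also be said that 7.1.2.1 asks for evidence of acute kidney injury and does not demand two scheduled samples. That is fair, but it is then defined by a rise within 7 days, and routine sampling cannot supply that evidence.

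**Conclusion.** The point holds as a defect in the wording of a safety rule. No pair of scheduled on-treatment samples can meet the creatinine limb: the shortest gap is 8 days between adjacent visits and 11 days from Day 0. A 1.5-fold rise first seen at a two-weekly visit does not trigger the numeric stop, and 7.1.2 directs continuation when eGFR is 30 to below 90, without excepting it. What is lost is the uniform trigger, not the ability to stop.

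The gap arithmetic rests only on the stated windows. The statement that most such rises miss the eGFR stop rests on the assumed eGFR relation; its range of k moves the limit only from 45 to 49. How often such a rise would occur cannot be derived from the documents: the healthy-volunteer studies summarised in 2.3.1 report no clinically significant laboratory changes.

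**What to change.** **Wording, in three places.**
- **7.1.2.1:** delete the 7-day limit and write: *serum creatinine at least 1.5 times baseline (Day 0 value, or screening value if none was drawn at Day 0), confirmed by a repeat within 7 days*. State that the criterion, and with it the 8.1.2 bar on restart, applies only on confirmation. State that pausing or reducing the drug until the repeat is for the study physician to decide under 6.6, 8.1.1 and 9.17.
- **Section 8 item 1:** use the same definition.
- **7.1.2:** except such rises from the continue action and refer to Section 8 items 2 and 3.

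The repeat interval should be given in days. Item 2 offers weekly or bi-weekly repeats, and 2.3.1 uses bi-weekly for the two-weekly visits. Writing *at least 1.5 times* also removes any doubt about what an increase by 1.5 times means.

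**Cost.** No new scheduled visit is needed, but each repeat is an extra unscheduled draw, which Section 9 and 9.15 already permit. There may be a few more pauses or permanent stops among 16 participants. One permanent stop is 1/4 = 25% of the donepezil arm or 1/12 = 8.3% of the phenserine arm, although Section 7 keeps participants withdrawn from treatment in follow-up. Requiring confirmation limits stops for transient rises such as dehydration.

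If the physician does pause for a full 7 days at 10 mg tds, 21 of 2 × 14 + 2 × 14 + 3 × 28 = 140 planned capsules are missed, leaving 119/140 = 85%. On donepezil 49/56 = 87.5% remain. Both are inside the 80–120% compliance range if no other dose is missed. The less visible cost is timing: a pause after Week 2 or Week 4 could delay escalation and shorten the four maintenance weeks intended in 6.6.
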